That population will yield a subset with advancing but asymptomatic disease. Within that sub-population a group will exist who will proceed to diagnosis and be willing to learn about clinical trials. By measuring this response the effectiveness of the messaging about engaging diagnosis and follow up can be shown. There is not comparable data so this will establish a baseline.

A separate track will be to measure the number of participants who enter the diet and lifestyle education programs. Measuring this response will also establish a baseline measure for the effectiveness of this messaging and inform future efforts.

Overview

Research has shown that there is a high incidence of undiagnosed fibrosis within comorbid populations as a result of the frequently asymptomatic course of NASH

development. (<https://www.ncbi.nlm.nih.gov/pmc/articles/PMC4542082/>)
Liver disease is a dangerous and expensive problem to manage medically with the cost of NAFLD estimated to exceed \$32 billion per year.

(<https://www.sciencedaily.com/releases/2018/07/180703105956.htm>)

Liver disease in the form of Nonalcoholic fatty liver disease (NAFLD) and nonalcoholic steatohepatitis (NASH) are rapidly increasing population health threats driven primarily by diet and lifestyle. Fibrotic liver disease, culminating in cirrhosis, is frequently asymptomatic so it is common for a patient to first learn of what is a life threatening condition by being told that they have cirrhosis. Management and treatment of cirrhosis is complex and very costly with few treatment options and the only current therapy being a very expensive transplant for end stage liver disease.

The position of the Fatty Liver Foundation is that this problem is magnified by the current American Association for the Study of Liver Disease, (AASLD), practice guidelines which do not advise routine screening for NAFLD. This is the policy:

Excerpts from the AASLD Practice Guidelines 2017:

(AASLD Diagnosis Mgt NAFLD Chalasani et al 2017 Hepatology)

- It can be argued that there should be systematic screening for nonalcoholic fatty liver disease, (NAFLD), at least among higher-risk individuals attending diabetes and obesity clinics.

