The primary patient outreach efforts will be to focus on high risk comorbid patients. We will communicate with local physicians to inform them that the service exists and invite them to refer appropriate patients to the screening facility or alternatively invite us to visit their offices with a portable unit.

The Foundation will also perform educational outreach through social media, communication through internet advertising, online forums, interaction with local support groups, media interviews and other educational efforts emphasizing the problem of our growing societal health crisis with obesity in general and liver disease in particular.

It is important to emphasize that during this study the FibroScan test will be free to qualified patients but they will be interviewed to ask what price they would be willing to pay on a private pay basis. This information will be used to perform the analysis of the viability of a private pay model. There will be no insurance or third party payment. Following testing the patient will be asked what payment amount, ranging from zero to more than \$400, would seem fair to them as a charge. The goal is to develop perceived value measures which can inform the financial modeling for the development of the fully deployed business plan.

Outputs of the project for the patient

All patients will receive education about liver disease as part of the intake process. Following the test, the patient will receive a printed output from their FibroScan test and instructions about next steps. Interpretation of test results require professional medical knowledge which is not provided by the study. Patients will be directed to a telemedicine system where they can discuss their results with professional staff and determine any next steps. Patients may elect to confer with their personal physician instead as is their right. Patients with test results indicating no active disease will be offered connections to nutrition and dietary support. In all cases patients will be offered enrollment in online educational tools about diet and lifestyle.

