- When any questions have been answered, the staff member will explain consent, provide the patient with the document, and answer any other questions.
- Upon signing of the consent the staff member will assign a random number to the consent and to the patient questionnaire.

Step 2: Data Capture

- After signing the consent form the patient will be asked to fill out the demographic form which will record basic health information, height, weight, sex, age, ethnicity, and identify any comorbid conditions of which they are aware from a list of common liver related comorbidities.

Step 3: The FibroScan test

- The patient will take the completed intake form and the educational materials with them to the FibroScan test room where the test will be performed.
- A certified FibroScan technician will double check the intake form and answer any additional questions that the patient may have.
- The technician will then administer the test according to the established standard test procedure and will identify it with the random number assigned to this test in step 1.

Step 4: Posttest process and instructions

- When the test is complete the test results will be printed out and given to the patient.
- The patient will also be given detailed information about how FibroScan is used and what it measures in a format that they can use to inform themselves so that they can better discuss the results and next steps with a physician. This will include explanations of how liver stiffness and fatty infiltration are defined and measured by the device.
- The patient will be asked to assess their perception of the value of the test to them personally by indicating what they perceive the value is of the test to them personally on a scale from nothing to over \$400.
- The patient will also be given printed information providing ways to contact resources and information about lifestyle changes, free support services, and information about how to access additional online tools.
- Most importantly, the patient will be instructed on how to access telemedicine support for interpretation of the test results and next steps. The technician will explain that the study provides the test, but interpretation must be done by a physician. Some patients may elect to discuss it with their existing doctor but

they will be encouraged to utilize the hepatology services, particularly if their test results are elevated.

Confidentiality

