- Starchy carbohydrates: breads, rolls, pasta, cereals, potatoes, rice, corn, peas, lima beans
- Non-starchy vegetables: lettuces, kale, carrots, green beans, broccoli, peppers, onions, cucumber
- Fats: butter, margarine, avocado, oils (olive, safflower, cottonseed, peanut, sesame, walnut)
- Nuts: peanuts, walnuts, cashews, almonds, macadamias, peanuts
- Sugars or Syrups: sugar, high fructose corn syrup (sodas), maple or corn syrups
- Fast food meals
- Eating out at restaurants

Exercise:

Subjects will fill out a form using a 5-point scale of the frequency of their average weekly exercise:

(A. 0 days, B. 1-2 days, C. 3-4 days, D. 5-6 days, E. 7 days per week) ○ Cardiovascular: brisk walking, jogging, biking, treadmill, stationary bike, stair stepper, elliptical, swimming laps ○ Strength: weight lifting, resistance machines or cords

Alcohol:

Subjects will fill out a form quantifying their average weekly total of alcoholic drinks:

(1 drink= 12 oz. beer, 6 oz. wine, 1.5 oz. hard liquor; 3 oz. brandy, sherry, liqueur):

- None
- 1-2 drinks/week
- 3-4 drinks/week
- 5-6 drinks/week
- 7-8 drinks/week
- 9-10 drinks/week
- 10-12 drinks/week
- 13-14 drinks/week
- 14-20 drinks/week
- 21 or more drinks/week

Other Liver Diseases:

Subjects will check YES or NO for other liver-related diseases that they may or may not have:

- Hepatitis B alone
- Hepatitis B with Hepatitis D
- Hepatitis C
- Hepatitis E
- Autoimmune hepatitis
- Primary biliary cholangitis
- Primary sclerosing cholangitis
- Iron overload
- Alpha-1-antitrypsin deficiency

Reporting of CAP-FibroScan Results to Participating Subjects:

A trained individual will perform the CAP-FibroScan according to the FDA-approved, manufacturer's protocol. A licensed hepatologist will determine the degree of fibrosis and will review the results and the steatosis based on the values in the following tables:

Transient Elastography (TE):

Disease	F0-F1	F2	F3	F4
NAFLD/NASH	≤ 7.0	≤ 7.5	≤ 10.0	≤ 14.0

Reference: Current Gastroenterology Reports. 2014; 16: 372

TE Interpretation: The subject's liver stiffness score in kPa units shows:

- **F0:** No liver fibrosis
- **F1-2:** Mild-Moderate liver fibrosis
- **F3:** Severe liver fibrosis
- **F4:** Cirrhosis

Controlled Attenuation Parameter:

Steatosis Grade	% Steatosis on Liver Biopsy	CAP Value
Mild (S1)	5-33%	225-275 dB/M
Moderate (S2) to Severe (S3)	>33% >66%	275-400 dB/M

Reference: World J Gastroenterol. 2016; 22: 7236

CAP-FibroScan Experience and Satisfaction Survey:

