 - No fat but evidence of liver stiffness
 - Fat without liver stiffness
 - Fat with liver stiffness
 - Stiffness values indicative of cirrhosis
 - Stiffness values indicative of fibrosis without cirrhosis

NOTE: no individual follow up or track will be done as not personally identifiable information will be captured or retained.

2. The secondary goal is to determine factors that are statistically significantly associated with the presence or absence of fat with or without increased liver stiffness.

We will analyze data using a standard statistical software package, Stata® 12.1 (Stata Corp, College Station, TX). We will express continuous variables using the mean ± standard deviation, and we will test the null-hypothesis using the Student t-test. We will compare categorical variables using contingency table analysis. For all statistical tests, we will define a two-sided p-value of ≤0.05 as statistically significant. We will perform multivariate analysis of all risk factors found to be statically significant (p ≤0.05) using univariate analysis.

This exploratory goal seeks to determine the degree of satisfaction of subjects who undergo a screening CAP-FibroScan free of charge.

We will calculate the frequency of answers for each of the five items reflecting subjects' likelihood of:

- recommending this test to a friend or family member.
- sharing their results with their doctor.
- consulting with a liver specialist.
- seeking information about FDA-approved clinical trials of therapies for non-alcoholic fatty liver disease.
-

We will not perform statistical analyses for these descriptive data.

Disease Staging

The disease staging to be analyzed will be based upon these breakpoints from the FibroScan test. The test scores will be translated into these staging ranges for analysis.

Transient Elastography (TE):

Disease	F0-F1	F2	F3	F4
NAFLD/NASH	≤ 7.0	≤ 7.5	≤ 10.0	≤ 14.0

Reference: Current Gastroenterology Reports. 2014; 16: 372

TE Interpretation: The subject's liver stiffness score in kPa units shows:

- **F0:** No liver fibrosis
- **F1-2:** Mild-Moderate liver fibrosis
- **F3:** Severe liver fibrosis
- **F4:** Cirrhosis

Controlled Attenuation Parameter:

Steatosis Grade	% Steatosis on Liver Biopsy	CAP Value
Mild (S1)	5-33%	225-275 dB/M
Moderate (S2) to Severe (S3)	>33% >66%	275-400 dB/M

Reference: World J Gastroenterol. 2016; 22: 7236

DATA COLLECTION

Demographics:

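### The plan asks how people with advancing or advanced disease respond, but reports the likelihood items only overall, and its result-dependent advice uses terms not linked to the staging tables

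*Combined protocol and SAP*

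**What the plan says.** **Who interprets.** The protocol, under *Outputs of the project for the patient*, states: "Interpretation of test results require professional medical knowledge which is not provided by the study". *Step 4: Posttest process and instructions* agrees: "The technician will explain that the study provides the test, but interpretation must be done by a physician". Under *Reporting of CAP-FibroScan Results to Participating Subjects*, however, "A licensed hepatologist will determine the degree of fibrosis and will review the results", using stiffness and CAP tables that the SAP repeats under *Disease Staging*. The hepatologist appears in none of the four visit steps.

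**What depends on the result.** *Outputs* says: "Patients with test results indicating no active disease will be offered connections to nutrition and dietary support". Step 4 says of participants that "they will be encouraged to utilize the hepatology services, particularly if their test results are elevated".

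**The survey.** It is given once participants have heard their results. Step 4 does not list it. Step 1 puts the random number on the consent and the patient questionnaire; *Confidentiality* names the consent and demographic forms. Neither clearly names the post-test survey.

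**The question asked.** *Hypothesis* expects some of those with advancing, asymptomatic disease to go on to diagnosis and to be open to information on trials, and adds: "By measuring this response the effectiveness of the messaging about engaging diagnosis and follow up can be shown". *Questions Posed by this Study* asks what share of asymptomatic people with advanced disease would want to learn about trials.

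**The analysis planned.** SAP *Data Analysis*: "We will calculate the frequency of answers for each of the five items". Four are printed: recommending the test, sharing results with a doctor, consulting a liver specialist and seeking trial information. No breakdown by scan result is listed. The same section says that "no individual follow up or track will be done as not personally identifiable information will be captured or retained".

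**The concern.** Two pieces of advice rest on a classification that no visit step assigns to anyone and that no stated value defines. What a person with given readings is told could therefore vary from visit to visit.

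This bears on the likelihood items. A person's stated intention to see a liver specialist plausibly depends on whether they understood the result to be raised, and on whether the survey came before or after the hepatology message. With no individual follow-up, the intent items are the only listed measure of moving towards diagnosis. The protocol wants that response as a baseline in people who have disease, whereas the listed output pools them with everyone else.

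**Working it through.** The plan gives no expected frequency or share on this point, so there is no figure of its own to reproduce. The check compares the text, then asks what an overall frequency can show.

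**1. Terms against tables.** As printed, the stiffness rows are F0-F1 ≤ 7.0, F2 ≤ 7.5, F3 ≤ 10.0 and F4 ≤ 14.0 kPa; CAP is 225-275 dB/m for S1 and 275-400 for S2-S3. Take 5.5 kPa with CAP 260: F0-F1 stiffness with S1 fat. The text does not say whether this is elevated or no active disease. Elevated stiffness could begin above 7.0, 7.5 or 10.0 kPa.

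**2. Question against output.** The question concerns people with advancing or advanced disease. The SAP output is one frequency per item for all participants. *Intended Use of the Data* also tracks the response to trial information and dietary support, but in aggregate and without reference to individual records. As described, that gives a count for everyone and no rate by result.

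**3. What an overall frequency reveals.** Let s be the share with elevated results, p_E their frequency and p_N that of the others:

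overall p = s·p_E + (1 − s)·p_N

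With p = 50% and s = 20%, p_N = (0.50 − 0.20·p_E)/0.80. If p_E = 0, p_N = 62.5%; if p_E = 100%, p_N = 37.5%. Both are possible, so the overall figure does not constrain the subgroup figure at all.

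**4. Dilution against sampling error.** Participant numbers (400 and 1,000) are the minimum and maximum in *Intended Use of the Data*. The share s of 10% to 30% is an assumption. The 95% half-width at p = 0.5 is 1.96·√(0.25/n): 4.9 points at n = 400 and 3.1 at n = 1,000. A change d in the elevated group's answers moves the overall figure by s·d, so the break-even is d = half-width/s.

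| s | d at n = 400 | d at n = 1,000 |
|---|---|---|
| 10% | 49.0 points | 31.0 points |
| 20% | 24.5 points | 15.5 points |
| 30% | 16.3 points | 10.3 points |

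Reported by band, the whole change d is visible.

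**5. Precision within the elevated group.** The same formula with n·s participants gives:

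| s | n = 400 | n = 1,000 |
|---|---|---|
| 10% | 40 people, ±15.5 points | 100 people, ±9.8 points |
| 30% | 120 people, ±8.9 points | 300 people, ±5.7 points |

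That is coarse but usable for a descriptive baseline. The cirrhosis band alone would be smaller; the documents give no basis for saying how small.

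**The case against.** The strongest reply is that little turns on the split. Everyone is told how to reach telemedicine and given lifestyle and support information, and online diet and lifestyle tools are offered to all. The 5.5 kPa participant gets nearly the same package under either label. The Step 4 steer can also be read as one conditional message given to everybody, with no sorting by staff. All of this stands, and it limits the harm.

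The likelihood items are exploratory, and the SAP says that they will not be tested. The break-even shifts show that the overall frequencies are fairly robust. That also stands, but robustness of the overall figure is another way of saying that it carries little information on the subgroup the protocol asks about.

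On linkage, the patient questionnaire coded in Step 1 might be meant to include the survey, and the SAP keeps all data in one worksheet with a number per subject. Either could supply the link, but neither says so. Step 1 comes before the intake form in Step 2, so the questionnaire is more naturally that form.

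A reader might infer more than the documents support:

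- *No cut-offs at all.* The tables exist; only their link to the two terms is missing.
- *No follow-up of any kind.* Uptake of trial and diet information is tracked in aggregate.
- *Participants with cirrhosis-range values leave without direction.* All are pointed to telemedicine or their own physician.
- *The handouts lack reference values, or the hepatologist's reading never reaches the participant.* The handouts are not in the text, and the timing of the reading is not stated.

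**Conclusion.** The point holds in a limited form and is an optional improvement. The protocol is inconsistent on who interprets results, and two result-dependent messages use terms with no stated value. The consequence for participants is modest because the main referral route is open to all.

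The consequence for analysis is clearer: the planned overall frequencies cannot answer the protocol's question about people with advancing or advanced disease. That follows from the algebra and needs no assumption about the size of the subgroup. The break-even range of 16 to 49 points (n = 400) or 10 to 31 points (n = 1,000) does rest on an assumed elevated share of 10% to 30% and a frequency near 50%.

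A reader might infer that the primary results are compromised. They are not: the proportions with fat, stiffness and cirrhosis-range values come from the scan and do not depend on what participants were told.

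**What to change.** 1. **Link and tabulate.** Put the existing ID code on the post-test survey and list the survey at one fixed point, the end of Step 4. Add one descriptive SAP table of the likelihood items by result band: no fat or stiffness; fat only; fibrosis-range stiffness; cirrhosis range. Give counts and, if wanted, 95% intervals, without tests.

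2. **Define the two terms by the same bands.** Print them on a one-page card, approved in advance by the hepatologist, marked as not being a diagnosis and handed over with the printout. The card needs decisions that the tables leave open: where raised stiffness starts (F0 and F1 share a row, while the interpretation list groups F1 with F2), an open-ended top (values above 14.0 kPa have no row as printed), and what CAP below 225 means. The double listing of CAP 275 does not matter here, since both grades count as fat.

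3. **Reconcile the text.** Make *Outputs* and *Reporting of CAP-FibroScan Results* agree on who interprets results, and when.

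The satisfaction boxes in survey question 2 can stay as they are; they record how well results were explained.

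Cost: one card page, a few sentences, a code on an existing form, one descriptive table with small counts in the top band, and an IRB amendment. No new visit, contact data or follow-up is needed.

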Patients will also be told about clinical trials and receive information about that process and offered access to online educational information and trial access tools if they are interested. Part of the outreach from the study is to educate patients about the need for clinical trials and to encourage learning more about it. The core message is that therapies will not be successful in the future without a cohort of patients who have been educated about clinical trials and are willing to consider participating. We will not recruit for any particular trials but will discuss their value and importance to society and potentially to individual patients.

By focusing on asymptomatic and undiagnosed liver disease the project will identify a currently unavailable population ideally suited for the upcoming clinical trials required for the development of therapies for liver fibrosis in NAFLD, NASH, and cirrhosis.

Study procedures

Testing will be done by appointment. Since the test itself is very fast, with a planned test throughput of 15 minutes, most of the visit will be taken up by the consent procedure, explanation of the test itself, discussion of liver disease, and distribution of literature.

When the test schedule is created, patients will be instructed not to eat within 3 hours of their appointment time so that a convenient time can be chosen.

There will be four steps in the process.

Step 1: Explanation and Consent

- At the intake point a staff members will explain the purpose for the study, provide information about liver disease, fatty liver, NASH, and fibrosis.
- The staff member will review the inclusion/exclusion rules and confirm that the patient has met the 3 hour fasting rule and has not been diagnosed with a liver disease.
- If inclusion criteria are met, the staff member will describe non-invasive testing process using the FibroScan, give the patient printed information, and explain that it measures both liver stiffness and fat content which their doctor can use to help them with any diagnosis that may be needed. It will be explained that FibroScan does not provide a diagnosis but is part of the information a doctor would use to understand the health of their liver. A sample test report will be used as a visual aid. Any questions will be answered.

- The staff member will explain what information will be gathered and explain that it is demographic information only and that no personally identifiable information will be collected.

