Under this protocol, no personally identifiable information will be captured. The consent form does require that it be personally signed but that information will not be digitized. Upon completion of the study the paper copy of the completed consent forms will be placed in secure storage.

The test will be assigned a randomly generated ID code which will be assigned to the consent form and to the demographic form. That code will connect the demographic information to the results of the test for analysis. In the event that a competent authority required the retrieval of the consent for the test, it would be possible, through the use of the ID code, to connect the information. At no time will the information be stored together or be in a compatible format.

The ID code will be keyed to the digitally stored FibroScan results database which the patient can provide to their physician at their discretion. The scans will not be personally identified and can only be accessed by the unique code. The dataset will be stored and encrypted and individual test results can only be retrieved using the random key code. In this way the patient can have access to the test result but only the patient will be in possession of the key that accesses the information.

Employees will be trained in the expectations of confidentiality and will have signed an agreement to keep any patient information private as part of the hiring procedure.

The FibroScan Test Procedure

FibroScan is notable for its fast, safe, non-invasive design. This is the procedure:

A certified FibroScan trained technician will administer the test.

- A pain-free diagnostic test, FibroScan® requires no sedation of any kind.
- The procedure itself usually takes about 5 minutes.
- For the procedure, the patient will lie on their back with their right arm raised behind their head and their right abdominal area exposed.
- The technician will apply a water-based gel to the skin and then place a non-invasive probe over the liver.
- During the exam, the patient may feel a slight vibration on the skin at the tip of the probe as it delivers ultrasound waves to the area for measuring purposes.

Risk/Safety Information

There are no uncommon risks or safety concerns resulting from this procedure. There will be the normal office space risks when accommodating patients with the common comorbidities

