 - The discussion provided useful information about FDA-approved clinical trials of therapies.
 - The discussion of my liver health will help me obtain better health care for my liver.
- b. If you answered dissatisfied or very dissatisfied, please check all the reasons for your answer:
- I do not understand what the CAP-FibroScan measures.
 - I do not understand how much fat I have within my liver.
 - I am not sure if I have or do not have scarring (fibrosis) of my liver.
 - The results did not give me a better understanding of my liver health.
 - The discussion did provide useful information about FDA-approved clinical trials of therapies.
 - The discussion of my liver health is unlikely to help me obtain better health care for my liver.

SUNN STUDY

STATISTICAL ANALYSIS PLAN

PRIMARY OUTCOME MEASURE – DETERMINE THE INCIDENCE AND STAGING OF UNDIAGNOSED NAFLD AND NASH IN A HEALTH CONSCIOUS SELF SELECTED POPULATION AS MEASURED WITH A FIBROSCAN

The study will measure the incidence and severity of the fat content and liver stiffness in an at large, self selected population who do not, at the time of testing, have a diagnosis of NAFLD, NASH or other liver disease. This will measure the incidence of undiagnosed liver disease and the statistical distribution of the disease staging in this population.

A key secondary outcome measure will be the incidence and disease distribution as a function of ethnicity.

We will analyze data using a standard statistical software package, Stata® 12.1 (Stata Corp, College Station, TX). We will express continuous variables using the mean \pm standard deviation, and we will test the null-hypothesis using the Student t-test. We will compare categorical variables using contingency table analysis. For all statistical tests, we will define a two-sided p-value of ≤ 0.05 as statistically significant. We will perform multivariate analysis of all risk factors found to be statically significant ($p \leq 0.05$) using univariate analysis.

Data Analysis

We will record all data in a Microsoft Excel worksheet. We will sequentially number each participating subject. We will not record any identifying information (e.g., names, initials, DOB, SSN, insurance, EPIC MRNs) in the database. Thus, all data assessments will maintain the anonymity of all participating subjects.

1. The primary goal is to calculate the proportion of men and women that when tested have CAP-FibroScan evidence of:
 - No fat or liver stiffness

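### Participants are told before signing that only demographic, non-identifiable data are collected, but the study records health data under a code that is also on the retained signed consent

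*Combined protocol and SAP*

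**What the plan says.** **Before signing.** Protocol, Step 1 (Explanation and Consent), has staff describe the information to be gathered, in the terms that "it is demographic information only and that no personally identifiable information will be collected". Once the consent is signed, the staff member will "assign a random number to the consent and to the patient questionnaire".

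**After signing.** In Step 2, "the patient will be asked to fill out the demographic form which will record basic health information, height, weight, sex, age, ethnicity", and participants also "identify any comorbid conditions of which they are aware from a list of common liver related comorbidities". In Step 3 the technician labels the scan with the number from Step 1. The Data Collection sections of the protocol and SAP list the form items in full.

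**Confidentiality.** This section opens by saying that nothing personally identifiable is captured. It then says that the consent is personally signed, is not digitized, carries the ID code and goes into secure storage when the study ends. If a competent authority required retrieval of a consent, "it would be possible, through the use of the ID code, to connect the information". The next paragraph says of the stored scan results that "only the patient will be in possession of the key that accesses the information".

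**SAP, Data Analysis.** On numbering: "We will sequentially number each participating subject". The note after the primary goal gives as its reason for having no individual follow-up that "not personally identifiable information will be captured or retained" (the first word is evidently meant as no).

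**The concern.** Two separate properties are promised: that the content is demographic, and that nothing can be traced to a person. If the plan delivers neither, participants hear a description of their data that the study's own procedures contradict, and they hear it when deciding whether to sign. They meet the health questions only afterwards.

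The two numbering schemes add to this. A random code is one of the protections the protocol relies on. An analysis file numbered in sequence either departs from it or needs a link to it that is not described.

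**Working it through.** No power or estimation arithmetic applies, and the plan states no figure to reproduce. The check is a count of form items and a comparison of statements.

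**1. Is the content demographic only?** Count of items in the Data Collection sections, with cancer taken as one heading:

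| Block | Items |
|---|---|
| Metabolic syndrome components (yes/no) | 6 |
| Other health conditions (yes/no) | 12 |
| Other liver diseases (yes/no) | 9 |
| Diet | 8 |
| Exercise | 2 |
| Alcohol (one item, ten levels) | 1 |

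Non-demographic items: 6 + 12 + 9 + 8 + 2 + 1 = 38. Yes/no health conditions: 6 + 12 + 9 = 27. Against these stand three demographic items (sex, age, race/ethnicity) plus measured height and weight. The 27 include heart attack, stroke, low testosterone, menopausal state, cancer by type, and hepatitis B, C and E. The scan result comes on top. The answer is no.

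**2. Is the information non-identifiable?** Following the code through the protocol:

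- Staff assign it and put it on the signed consent and the questionnaire (Step 1, Confidentiality).
- The technician puts it on the scan (Step 3).
- It joins the form to the scan for analysis (Confidentiality).
- The signed consent bearing it is stored (Confidentiality).

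So the study holds a signature and a code on one document, and the code with the health and scan data elsewhere. Confidentiality confirms that the two can be connected. That is coded, re-linkable data.

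**3. Which statements conflict with this?**

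| Statement | Conflicts with |
|---|---|
| Step 1: demographic only | Step 2 and the Data Collection lists |
| Step 1 and Confidentiality: nothing identifiable collected or captured | Signed, coded consent that is kept |
| Confidentiality: patient alone has the key | Code on the study's consent, questionnaire and scan; re-linking route one paragraph earlier |
| SAP note: nothing identifiable captured or retained | Stored signed consents |

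**4. Numbering.** The SAP does not say whether the sequential number replaces the random code, sits beside it, or is only a row label. If it replaces the code, the dataset no longer uses the identifier described in the protocol. If it sits beside the code, a link between the two exists and is not described. If it is a row label in no particular order, it is harmless, but the SAP does not say so.

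**The case against.** The strongest reply has four parts.

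- **Loose labelling.** Demographic form is the protocol's name for the whole intake form, and Step 2 says openly that it records health information. Eligibility already turns on self-reported chronic conditions, which staff review before consent, so participants know that health is involved. This softens the first half of the contradiction without removing it. Cancer, alcohol and diet are not eligibility criteria, and a participant listening to staff does not have Step 2 to hand.
- **Disclosure and safeguards.** Confidentiality states the re-linking route and ties it to a competent authority's demand. Consents stay on paper, are stored apart from the data and in no compatible format, the dataset is encrypted, the system is HIPAA compliant, and staff sign confidentiality agreements. All of this stands, and a reader should not infer concealment. These measures lower the chance of disclosure; they do not make what participants are told accurate.
- **Narrow context.** The key sentence concerns the scan database, and the SAP note explains why there is no follow-up. That is a fair reading of their purpose. The study nevertheless holds the same code that opens the scan record, and the note's reason is worded without limit.
- **The consent form.** It is not in the supplied text and may be accurate. A reader might infer that consent is obtained on a wrong written description; the documents cannot show that. The finding covers the prescribed oral explanation and the protocol and SAP text. If the form is accurate, staff would be contradicting it.

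**Conclusion.** The point holds as a contradiction between what participants are to be told and what the plan does. It affects every participant. The protocol seeks at least 400 and allows up to 1,000, but recruitment also stops at three months, so 400 is a target and not a guaranteed minimum. The conclusion rests on the code being placed and the consents kept as the protocol describes.

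Three stronger readings are tempting, and the documents do not support them:

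- **That this is the study's main non-physical risk.** The Risk/Safety section does not mention confidentiality, but nothing in the documents ranks such risks.
- **That sequential numbers can be matched to the appointment list.** Testing is by appointment, but the SAP does not say that numbers follow enrolment order, and no section says that a named list is kept. This is a possibility only. The mismatch between sequential and random numbering is what the text shows.
- **That the primary outcome is affected.** No bias, estimate or analysis is shown to change.

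**What to change.** - **Step 1 and Confidentiality:** say that coded health, alcohol, diet, exercise and scan data are collected, that the signed consent carries the same code and is kept, and that re-linking is possible under the conditions already stated. Remove or correct the blanket statements that nothing identifiable is collected or captured.
- **Key sentence:** delete it, or limit it to what is true of access to the scan database.
- **SAP note:** give the absence of individual follow-up as a design decision, and confine the no-identifiers statement to the analysis database.
- **SAP numbering:** use the protocol's random ID as the only subject identifier in the dataset.
- **Consent form:** check that it says the same as the revised text.

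The cost is an IRB amendment to wording and a small change to the data file. Some participants may decline items once these are described accurately. No endpoint, test or sample size changes.
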